Cox regression (Score Test) will be used to compare the experimental versus the control arms adjusted by the stratification factors in randomization (except for centers) at 1-sided 10% significant level.

Toxicity

Analysis for toxicity is based on the safety population. The worst grade of toxicity/adverse events observed over the whole treatment period (excluding re-challenge period for Arm A) according to CTCAE version 4 will be displayed. No formal statistical analysis will be performed to compare toxicity in both arms.

Response Rate

Patients with response categories progression, early death and unknown will be considered as failing to respond to treatment. The response rates in each arm and their 95% confidence intervals will be provided. In addition, response rates in the 2 arms will be compared using a two-sample test at 5% 2-sided level.

Translational research

The translational research is mandatory for this protocol. Any patient who consent to enter the trial will have to consent for the translational research.

Objectives

The main objectives of translational research study are, but not limited to, the following:

 to describe quantitatively the presence of T790M EGFR mutations and original activating EGFR mutations in plasma of patients treated with

- gefitinib and osimertinib longitudinally within the arms and to compare the presence of these mutations across the arms A, B and C.
- to describe the associations between the presence of these mutations and response evaluations by RECIST 1.1 longitudinally within the arms.
- to describe the associations between the presence of these mutations and response and PFS to osimertinib in Arm A, B and C.
- to assess mechanisms of resistance to osimertinib in formalin-fixed paraffin-embedded (FFPE) samples obtained from patients at baseline and at the time of progress on osimertinib by next generation sequencing and compare the presence of molecular resistance alterations in tissue samples and plasma samples taken on progression.

Human Biological material

- plasma sample taken during screening visit and each treatment visit (every 4 weeks) while patients are within active treatment with gefitinib or osimertinib. Note: if gefitinib or osimertinib is temporarily discontinued due to toxicity, plasma sample should still be obtained. The last plasma sample should be taken from patients who progress on osimertinib by RECIST 1.1 evaluation (all three arms).

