4.1 Treatment beyond progression

The local investigator may choose to continue treatment with osimertinib beyond RECIST 1.1 PD, if, in their opinion, the patient continues to receive clinical benefit. However, this should be discussed with the EORTC HQ. Information on post-PD treatment needs to be provided to EORTC HQ and follow-up must follow chapter 6 according to the treatment arm.

In case of oligo-progressive disease (please refer to chapter 0) in a known metastatic lesion local therapy (radiotherapy / surgery / cryotherapy) will be allowed after mandatory discussion with EORTC headquarters. This procedure will be reported in the CRF. Information on post-PD treatment needs to be provided to EORTC HQ and follow-up must follow chapter 6 according to the treatment arm.

5 Therapeutic regimens, expected toxicity, dose modifications

Osimertinib (AZD9291) and gefitinib are considered as Investigational Medicinal Products.

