5.3 Initial dose and schedule

Advanced EGFR mutant NSCLC and EGFR-TKI naïve patients, will be randomized to:

- Arm A: osimertinib 80 mg QD until RECIST 1.1 progression.
- Arm B: gefitinib 250mg QD until cfDNA T790M positive test (criteria for defining progression disease), irrespective of RECIST 1.1 criteria, then patients will receive osimertinib 80 mg QD until RECIST 1.1 progression. If patients have RECIST 1.1 progression without cfDNA T790M positive test, they will be switched to osimertinib.
- Arm C: gefitinib 250mg QD until RECIST 1.1 progression, irrespective of cfDNA T790M test, then patients will receive osimertinib 80 mg QD until RECIST 1.1 progression.

Continuation of osimertinib post-PD is allowed on individual basis provided that in the opinion of treating physician, patient may benefit from this therapy (please refer also to section 4.1).

Osimertinib or gefitinib must be swallowed with a glass of water and must not be mashed or chewed. The tablets can be taken preferably in the morning with or without meals

The initial dose of osimertinib 80 mg once daily can be reduced to 40 mg once daily. The initial dose for gefitinib (250 mg once daily) cannot be reduced to a lower dose.

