5.6.1 Osimertinib

All patients start treatment with osimertinib at 80 mg daily irrespective if the patient received osimertinib as first-line treatment or as sequential treatment after gefitinib. Only 1 dose reduction with osimertinib (to 40 mg) will be allowed during the study.

If a patient experiences a CTCAE grade 3 or higher and/or unacceptable toxicity (any grade) not attributable to the disease or disease-related processes under investigation, where the Investigator considers the AE of concern to be specifically associated with the study drug dosing will be interrupted and supportive therapy administered as required in accordance with local practice/guidelines.

If the toxicity resolves or reverts to ≤CTCAE grade 2 within 3 weeks of onset, study drug may be restarted at the same dose (starting dose) or a lower dose (40 mg) using the rules below for dose modification (Table "Recommended dose modifications with osimertinib). There will be no individual modifications to dosing schedule in response to toxicity, only potential dose reduction or dose interruption. If restarting at the same dose level, patients should be closely monitored for 3 days following the restart of treatment. If within 3 days there is recurrence of same toxicity, a dose reduction should be considered at the Investigator's discretion.

If the toxicity does not resolve to ≤CTCAE grade 2 after 3 weeks of withholding osimertinib, then the patient should be withdrawn from the study treatment and observed until resolution of the toxicity. There will be no individual modifications to treatment schedule in response to toxicity, only potential dose reduction or dose interruption.

If an AE subsequently requires dose interruption, study drug may restart at the same dose or the reduced dose, on resolution/improvement of the AE at the discretion of the investigator as described above.

Recommended dose modifications with osimertinib

Target Organ	Adverse reaction	Modification
Pulmonary	Interstitial lung disease (ILD)/Pneumonitis	Permanently discontinue osimertinib
Cardiac	QTc† interval greater than 500 msec on at least 2 separate ECGsb	Withhold osimertinib until QTc interval is less than 481 msec or recovery to baseline if baseline QTc is greater than or equal to 481 msec within 3 weeks of withholding osimertinib, then resume at 40 mg dose or at 80 mg (at the discretion of the investigator, to allow for situations where causality in relation to osimertinib may be difficult to determine)

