7.3 Evaluation of safety

7.3.1 Adverse events

All adverse events will be recorded; the investigator will assess whether those events are related to osimertinib (reasonable possibility, no reasonable possibility) or gefitinib (reasonable possibility, no reasonable possibility) and this assessment will be recorded in the database for all adverse events.

The collection period will start from randomization and all adverse events must be followed until resolution or stabilization.

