8.2 Statistical analysis plan

Analyses described below will be done separately for each arm, except for the secondary endpoint BPFS where comparisons between the arms (i.e. A vs. B, B vs. C and A vs. C) will be conducted.

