8.2.2 Statistical methods

Analysis of the primary endpoint

The primary analysis will be performed to per-protocol population.

Patients with success is defined by the primary endpoint in Section 7.2.1. The PFSR-OSI-18 in each arm and their 84% confidence intervals will be provided. In case the number of patients analyzed in each arm exceeds or less than what is foreseen above (Section 8.1.1), the 84% confidence interval will be used for the decision.

Time to event endpoints

The analyses of the primary and secondary endpoints will be performed on per-protocol population. Comparison between arms are foreseen for BPFS endpoint only.

Estimates and confidence intervals

Estimates of the median PFS-OSI, TTP-OSI, PFS2-OSI and OS are obtained by the Kaplan Meier technique. The 84% and 95% confidence intervals (CI) for the median will be calculated using the reflected CI method.

Estimates of the event-free rate at fixed time point (18 months) will be obtained using the Kaplan Meier technique and 84% 2-sided CI will be calculated by Greenwood's estimation of the standard deviation. Estimates of hazard ratios and their 84% 2-sided CI will be obtained by Cox regression. In addition 95% 2-sided CI will be provided for both the estimates of event rates and hazard ratios. Kaplan Meier Curves will be drawn for both the experimental and control arms on the same plot.

Inference: Test statistics for comparisons (for BPFS)

Cox regression (Score Test) will be used to compare the experimental versus the control arms adjusted by the stratification factors in randomization (except for centers) at 1-sided 10% significant level.

Toxicity

Analysis for toxicity is based on the safety population. The worst grade of toxicity/adverse events observed over the whole treatment period (excluding re-challenge period for Arm A) according to CTCAE version 4 will be displayed. No formal statistical analysis will be performed to compare toxicity in both arms.

Response Rate

Patients with response categories progression, early death and unknown will be considered as failing to respond to treatment. The response rates in each arm and their 95% confidence intervals will be provided. In addition, response rates in the 2 arms will be compared using a two-sample test at 5% 2-sided level.

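### The worst-grade toxicity display leaves out an undefined re-challenge period in arm A only, and Section 8.2.2 plans no table by drug for arms B and C

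*Combined protocol and SAP*

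**What the plan says.** Under Toxicity, Section 8.2.2 bases the analysis on the safety population and shows the worst CTCAE grade "observed over the whole treatment period (excluding re-challenge period for Arm A". The protocol summary carries the same rule: "excluding re-challenge period for Arm A) according to CTCAE version 4 will be displayed". Section 8.2.2 adds: "No formal statistical analysis will be performed to compare toxicity in both arms". Section 8.2 sets the frame: "Analyses described below will be done separately for each arm, except for the secondary endpoint BPFS".

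The regimen for the arm concerned is a single drug (Section 5.3): "Arm A: osimertinib 80 mg QD until RECIST 1.1 progression". Arms B and C receive gefitinib and then osimertinib.

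Two provisions resemble a re-challenge, though neither uses the word:

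- Section 5.6.1, on resolution of toxicity within the stated time: "study drug may be restarted at the same dose (starting dose) or a lower dose (40 mg".
- Section 4.1: "The local investigator may choose to continue treatment with osimertinib beyond RECIST 1.1 PD". Section 5.4 repeats this permission for each of the three arms.

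On data collection, Section 7.3.1 states: "The collection period will start from randomization and all adverse events must be followed until resolution or stabilization". It also has the investigator record relatedness to osimertinib and to gefitinib separately. Section 7.3.2 calls for non-hematological effects to be reported separately by study medication administration, and refers to the statistics section for the tabulations.

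**The concern.** An exclusion written for one arm of a randomized trial needs a defined period and a reason that is specific to that arm. Here there is neither. If some patients do have a period that could be called a re-challenge, the analyst must choose its limits after open-label data have accrued, and only in the upfront-osimertinib arm.

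Safety is a secondary endpoint (Section 2.4.2), and Section 1.4 asks whether osimertinib is better given upfront or in sequence. With no formal toxicity comparison planned, readers will set the descriptive columns side by side, so the windows should match. Readers will also want the osimertinib part of arms B and C next to arm A. A single worst grade over a two-drug sequence does not give them that.

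**Working it through.** **1. No plan figure to reproduce.** The toxicity rule has no sample size, alpha or power attached to it. The check is a comparison of sections, followed by the direction of the effect.

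**2. Can the term be tied to something specific to arm A?**

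| Candidate meaning | Where | Arms |
|---|---|---|
| A re-challenge step in the regimen | Sections 5.3 and 5.4 | None: arm A has no such step |
| Restart after a toxicity interruption | Section 5.6.1 | All: the section covers first-line and sequential osimertinib |
| Osimertinib beyond progression | Sections 4.1, 5.3, 5.4 | All: Section 5.4 states it arm by arm |

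The word occurs only in Section 8.2.2 and in its copy in the summary. No candidate explains a rule limited to arm A.

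**3. Direction.** For one patient and one type of event, let W be the full treatment window and W′ the window with some period removed, so that W′ lies inside W. Then max grade over W′ ≤ max grade over W. It follows that, for any grade threshold, the number of arm A patients shown at or above it can fall or stay the same, but cannot rise. Arms B and C keep the full window.

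**4. Scale, as an illustration only.** The documents do not give the share of arm A exposure that would be removed. Call it f and treat it as an assumption. With a constant hazard and a full-exposure probability P of at least one grade 3 or higher event, the displayed probability is 1 − (1 − P)^(1 − f). Section 1.3 gives P = 29.4% from the osimertinib phase II studies; 20% and 40% are assumed values on either side.

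| P | f = 0 | f = 10% | f = 20% | f = 30% |
|---|---|---|---|---|
| 20% | 20.0% | 18.2% | 16.3% | 14.5% |
| 29.4% | 29.4% | 26.9% | 24.3% | 21.6% |
| 40% | 40.0% | 36.9% | 33.5% | 30.1% |

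For the nine cells with f above zero, the fall runs from 1.8 to 9.9 points. If f = 0 the fall is zero. This is not an estimate of bias, because nothing in the documents supports any particular f.

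**5. Reporting by drug.** Section 7.2.7 runs treatment duration in arms B and C to the end of osimertinib, so the whole treatment period there naturally covers both drugs. Section 7.3.2 sends the reader to the statistics section for tabulations, and Section 8.2.2 contains only the one worst-grade display. The wording of Section 7.3.2 could mean by drug or by dosing occasion. On either reading, no matching table is planned.

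**6. End of the window.** Adverse events are collected at the visit 30 days after last protocol treatment (Sections 6.1.3, 6.2.4, 6.3.4), and all SAEs are reported to the same point (Section 14.6). Section 8.2.2 does not say whether events in those 30 days count as within the treatment period.

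**The case against.** The strongest reply is that the phrase may exclude nothing. The protocol calls a return to dosing a restart or resumption, and treatment past progression a continuation. It calls neither a re-challenge. A term that matches no step may be leftover wording with no patients behind it. That is possible, and in that case the effect is zero. It is also a reason to remove the phrase, since deletion then changes nothing.

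Second, a reader might infer a size from Section 1.3: with 11.7% of patients having a related grade 3 or higher event, 52 × 0.117 = 6.1, or about 6 of 52 arm A patients losing events. The documents do not support this. It counts patients likely to be interrupted, not table entries that change. The event that triggers the interruption precedes any restart and stays in a worst-grade display, so only a higher grade or a different event afterwards would alter it. Some interrupted patients would never restart, because Section 5.6.1 requires permanent discontinuation for several toxicities.

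Third, a reader might infer that fatal or late events disappear. They do not. Toxic deaths have their own evaluation (Section 7.3.4). SAEs are reported to day 30, and related ones after that (Section 14.6). Section 7.3.5 monitors severe related toxicity without any such exclusion.

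Fourth, one worst grade over the whole sequence suits a trial of delivery strategies, and no between-arm toxicity test is planned. That stands as a reason to keep the overall column. It is not a reason for unequal windows, or for omitting the by-medication reporting that Section 7.3.2 announces.

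Finally, it can be said that defining the period would be enough. A definition would cure the ambiguity, but not the asymmetry if the same period can occur in arms B and C.

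**Conclusion.** The point holds in a limited form. The plan contains a rule that applies to arm A only, rests on an undefined period, and can move arm A's displayed worst grade in one direction only. No bias has been shown. The effect depends on whether any patient has such a period and on what happens in it, and it may be zero. It would be wrong to conclude that the table will make upfront osimertinib look safer; the text supports only that it could.

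It would also be too strong to say that osimertinib toxicity in arms B and C cannot be set beside arm A. Relatedness by drug is recorded and Section 7.3.2 foresees reporting by medication, so the gap is that Section 8.2.2 plans no such table. Even with that table the comparison stays descriptive, because osimertinib is first-line in arm A and follows gefitinib in arms B and C.

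This affects a secondary, descriptive safety output and not the primary endpoint. It should be corrected before the tables are finalized.

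**What to change.** 1. Delete the parenthesis that excludes the arm A re-challenge period, in Section 8.2.2 and in the protocol summary.
2. State one display window for all arms: first dose of protocol treatment to 30 days after last protocol treatment. This matches the end-of-treatment visit and the end of the period in which all SAEs are reported. Say explicitly that restarts and osimertinib beyond progression are included.
3. For arms B and C, show the worst grade for the gefitinib phase, the osimertinib phase and overall, and say how events are assigned to a phase (for example, by the date the grade was reached relative to the first osimertinib dose).
4. Correct the reference to two arms in the sentence on toxicity comparison, since the trial has three.

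The cost is a change of SAP wording and two extra columns, one per drug phase, for arms B and C. No new data are needed. The only downside is that arm A toxicity may look slightly less favourable than under the present rule.

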8.2.3 Pre-planned sensitivity or exploratory analyses

A sensitivity analysis of efficacy based on intent to treat (ITT) population will be conducted in addition to the primary analysis based on per protocol population.

Sensitivity analyses will be conducted on PFS-OSI rate at 18 months according to RECIST 1.1 (primary endpoint) to verify the robustness of the results vis-à-vis the missing data. Once the main analysis is completed, PFSR-OSI-18 will be analyzed as binary endpoint. The following sensitivity analyses will be conducted:

- Patients lost-to-follow up before 18 months, i.e. with missing assessments at 18 months (using the window of ± 2 weeks) and at all times thereafter will be considered as having an event at 18 months (worst case scenario). Only patients with the confirmation they are alive and progression free at 18 months (status for PFS not missing at 18 months or after and status at 18 months is no progression) will be considered event free at 18 months.
 In details,
 - Patients alive and without any progression by RECIST 1.1 at 18 months will be counted as a success irrespective of treatment(s) received (still under protocol treatment or switched to investigator's choice standard treatment including no further systemic anticancer therapy documented).
 - Patients who progress on gefitinib by RECIST 1.1 or by positive cfDNA T790M status testing prior
 to 18 months and are switched to osimertinib (T790M positive) and progression free at 18 months
 after switching to osimertinib will be counted as a success.
 - Patients who progress on gefitinib by RECIST 1.1 or by positive cfDNA T790M status prior to 18 months and are switched to osimertinib (T790M positive) and progress by RECIST 1.1 after switching to osimertinib prior to 18 months will be counted as a failure.
 - Patients with a progression by RECIST 1.1 prior to 18 months and not able to start osimertinib prior to 18 months for any reason will be counted as a failure.
- Complete case analysis: the analysis will be restricted to patients with available PFS data at 18 months (complete case analysis).

In addition, sensitivity analyses will be conducted in which patients who will have started any other cancer treatment before their disease progresses will be considered as having an event at the date of start of the other cancer treatment.

Exploratory analysis of BPFS and OS according to the presence of T790M mutation status and the presence of original activating EGFR mutation in the plasma will be performed. In addition, exploratory endpoint on change in tumor size (see chapter 7) will be performed.

8.2.4 Prognostic factor analyses

No prognostic factor (PF) analyses will be conducted.

8.2.5 Data recoding and display

Frequency tables will be tabulated (by treatment group or otherwise) for all categorical variables by the levels of the variables as they appear on the CRF (with %). Categories with a text field specification will be tabulated as categories and then supplemented by a listing with the following information for the patients fulfilling the condition for the specification (patient id, institution, treatment group, value of the item and text field contents).

Dates relating to events prior to entry will be presented as the delay in days (or weeks, months, or years) between the past event and the date of entry (date of randomization – date of past event + 1) and presented using the median and range. For example, on the randomization checklist, the date of last administration of prior treatment (or the date of first diagnosis of the cancer) will be presented as the time elapsed (in days, weeks, months or years, as appropriate) since the day of the last administration and the date of entry on study (date of randomization – last administration/diagnosis +1).

Other delays (e.g. re-treatment delays) are presented as continuous variables using the median and range.

Continuous variables for which a coding system exists (such as for laboratory data) will be recoded into categories (for adverse events, the grading scale specified in the protocol will be used). Whenever no specific scale exists, lab data will be categorized based on the normal range: for example, below the lower normal limit (when appropriate), within the normal range, above the upper normal limit (ULN) and the degree to which it is above the ULN (for example > 2.5 x ULN, > 5 x ULN, > 10 x ULN). For laboratory data, the nadir is generally displayed. The nadir in a given cycle is the lowest laboratory value in that cycle; the overall nadir for a patient is the lowest laboratory value among all cycles.

Other continuous variables (for example age, dose ...) are presented using the median and range (minimum, maximum).

DI observed =
$$\left[\frac{mg}{m^2 \times weeks}\right] = \frac{total \ dose \ \left[\frac{mg}{m^2}\right]}{total \ duration \ \left[weeks\right]}$$

The relative dose intensity is calculated as the ratio of the dose intensity as calculated above to the dose intensity indicated in the protocol. The dose intensity indicated in the protocol is obtained as the dose specified per cycle (in mg/m^2).

The dose intensity and the relative dose intensity are presented using median and ranges. The relative dose intensity can also be presented in categories (≤70%, >70-90%, >90-110%, >110-120%.

If appropriate, continuous data may also be presented in categories (for example, age may also be grouped in decades).

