6.1 Arm A

6.1.1 Before randomization

Baseline assessments need to be performed within 21 days prior to randomization:

- Signature of the informed consent;
- Assessment of eligibility criteria;
- Assessment of the baseline signs and symptoms and adverse events based on CTCAE version 4.0, performance status and medical history;
- Collection of concomitant medication;
- Demographics, physical examination, including vital signs, height, weight and blood pressure;
- Laboratory examination including:
 - hematology: white blood cell (WBC) with differential count, platelets (PLTs), hemoglobin (Hb);
 - biochemistry: blood urea nitrogen (BUN), serum creatinine and calculated creatinine clearance (by Cockcroft), uric acid, albumin, total bilirubin, Alkaline Phosphatase (AP), Aspartate AminoTransferase (AST/ASAT), Alanine AminoTransferase (ALT/ALAT), Gamma-Glutamyl Transferase (GGT), sodium, potassium, Lactic Dehydrogenase (LDH), total calcium, phosphorus, magnesium, glucose;

Note: * Electrolyte abnormalities (hypokalemia, hypomagnesaemia, hypocalcemia) must be corrected to be within normal ranges prior to first dose and electrolyte levels monitored during study treatment.

- Beta HCG (serum) for women of childbearing potential. This test must be negative within 72h before first dose of treatment;
- Stick urinalysis;
- Digital ECG with QTc interval; no alteration in QTc interval should be reported before osimertinib initiation:
- LVEF assessed by MUGA or ECHO
- Collection of plasma sample for central T790M status;
- Collection of tumor sample for translational research (please refer to section 10.2);
- Thoracic and upper abdomen contrasted-enhanced CT scan (including adrenal glands) and brain CT scan; if a patient is allergic to contrast adequate premedication as per local practice should be provided. Should there be any further constraint, the EORTC Headquarters should be contacted as soon as possible.
- Ophthalmological examination;
- Geriatric G8 assessment for 70 years old patients or older.

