7.3.2 General evaluation of adverse events

This study will use the International Common Terminology Criteria for Adverse Events (CTCAE), version 4.0, for adverse event reporting. A copy of the CTCAE can be accessed from the EORTC home page https://www.eortc.be/services/doc/ctc/.

Hematological toxicity will be assessed on the basis of regular blood tests. The nadir count will be computed at each study medication administration and graded according to the CTCAE version 4.0.

Non hematological acute side effects will be assessed and reported separately for each study medication administration, and graded according to the CTCAE version 4.0.

Planned safety analysis and tabulations are described in the statistics section.

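### Section 8.2.5 displays the lowest laboratory value with no exception for tests where high is harmful, so biochemistry tables can understate liver and renal abnormalities

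*Combined protocol and SAP*

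**What the plan says.** Section 8.2.5 (Data recoding and display) sets the convention for laboratory data in three steps.

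- Where a coding system exists, values are recoded into categories: "for adverse events, the grading scale specified in the protocol will be used".
- Where no scale exists, values are grouped around the normal range, including "above the upper normal limit (ULN) and the degree to which it is above the ULN". The examples given are above 2.5, 5 and 10 x ULN.
- Then comes the display rule: "For laboratory data, the nadir is generally displayed". It is defined at two levels: "The nadir in a given cycle is the lowest laboratory value in that cycle", and "the overall nadir for a patient is the lowest laboratory value among all cycles".

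The data concerned are listed in section 6.1.1. Besides blood counts, the panel includes "serum creatinine and calculated creatinine clearance (by Cockcroft), uric acid, albumin, total bilirubin", followed by alkaline phosphatase, AST, ALT, GGT, LDH, electrolytes and glucose. Later visits in all three arms refer back to this list.

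Two other sections bear on the point. Section 7.3.2, on hematological toxicity, says: "The nadir count will be computed at each study medication administration and graded according to the CTCAE version 4.0". Section 8.2.2, under Toxicity, displays for the safety population "The worst grade of toxicity/adverse events observed over the whole treatment period", leaving out the re-challenge period in arm A.

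**The concern.** A nadir is a worst-case summary only for tests where a low value is the harmful one. For liver enzymes, bilirubin and serum creatinine the harm lies in high values, so a patient's lowest value is the most reassuring one on record. The plan gives no highest-value or worst-value rule for laboratory values to balance this. A programmer who follows section 8.2.5 literally would produce biochemistry tables that make liver and renal findings look milder than they were. Safety is a secondary objective and endpoint (sections 2.2 and 2.4.2), and readers would use those tables descriptively.

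**Working it through.** The plan states no figure that can be reproduced here. The check compares the passages and adds one arithmetic fact.

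**1. Direction of harm, from the protocol's own limits.** The entry criteria in section 3.1.2 set upper limits for ALT and AST (2.5 x ULN, or 5 x ULN with liver metastases), total bilirubin (1.5 x ULN, or 3 x ULN with Gilbert's syndrome or liver metastases) and serum creatinine (1.5 x ULN). They set lower limits for neutrophils, platelets, hemoglobin and creatinine clearance (50 mL/min). The panel therefore mixes both directions. Alkaline phosphatase, GGT and LDH have no entry limit; that high is the harmful side for them is ordinary clinical reading.

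**2. What the displayed value can show.** Take values x1, ..., xk and a cut-off c above the ULN.

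- The lowest value exceeds c only if every xi exceeds c.
- The highest value exceeds c if any xi exceeds c.

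One normal result is therefore enough to take a patient out of every above-ULN category when the overall nadir is displayed.

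**3. Example (invented values).** ALT is 0.8, 6.0 and 1.2 x ULN over three cycles. The minimum is 0.8, which is not above the ULN. The maximum is 6.0, which falls in the category above 5 x ULN.

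**4. Size of the gap under simple assumptions, none from the documents.** Suppose six four-weekly values (24 weeks / 4 weeks = 6), independent, each with probability p of exceeding c. Then P(highest exceeds c) = 1 - (1 - p)^6 and P(lowest exceeds c) = p^6.

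| p | Highest exceeds c | Lowest exceeds c |
|---|---|---|
| 0.05 | 1 - 0.95^6 = 26% | 0.05^6 = 0.0000016% |
| 0.10 | 1 - 0.90^6 = 47% | 0.10^6 = 0.0001% |
| 0.20 | 1 - 0.80^6 = 74% | 0.20^6 = 0.0064% |

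Real values are correlated within a patient, so the true gap is smaller. Its direction cannot reverse, because a minimum never exceeds a maximum.

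**5. Which level of nadir does the damage.** A cycle is 28 days (section 6), and the detailed schedules plan laboratory tests every 4 or 8 weeks. With a single draw in a cycle, the per-cycle nadir is simply that value and nothing is lost. The problem lies in the overall per-patient nadir, and in cycles with repeat draws.

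**6. Where the rule is right.** Section 7.3.2 uses the nadir for blood counts, where lowest is worst. The same holds for creatinine clearance and albumin. Section 8.2.5 applies the term to laboratory data in general without adding the opposite direction.

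**The case against.** The case for leaving the text alone has four parts.

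- *The rule is a default.* The wording says the nadir is displayed generally, which leaves room for exceptions, and an analyst is unlikely to fill above-ULN categories with minimum values. The first part stands: the text does not impose the lowest value on every test. But no exception is named, so the choice falls to whoever programs the tables, and the only definition available gives the wrong one.
- *Toxicity is analyzed elsewhere.* This is the strongest point. Section 8.2.2 displays the worst grade, section 14.1 counts an abnormal laboratory finding as a possible adverse event, section 7.3.1 requires all adverse events to be recorded, section 14.3 has them graded by CTCAE v4.0, and section 7.3.5 monitors grade 3-4 non-hematological toxicity at least possibly related to treatment. An elevation reported as an adverse event therefore appears at its worst grade. What remains is that no section clearly says worst grades are also derived from biochemistry values that nobody reported as adverse events.
- *The ULN categories may not apply to ALT.* They are a fallback for tests without a specific scale. CTCAE is not reproduced in the documents, so whether the fallback covers ALT is an assumption. The answer does not rescue the rule, because grading a minimum gives the mildest high-side grade on any scale.
- *The numbers are invented.* This is true. They show a direction, not an expected error in this trial.

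A reader might infer that the plan uses the lowest value for every test and so hides hepatic and renal toxicity. The documents do not support that: the rule is qualified, it is correct for creatinine clearance, and the worst-grade display in section 8.2.2 is untouched.

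**Conclusion.** The display rule in section 8.2.5 is wrong as written for tests where high values are harmful: ALT, AST, bilirubin, alkaline phosphatase, GGT, LDH and serum creatinine. For these it shows the least abnormal value and conflicts with the above-ULN categories in its own paragraph.

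The consequence is limited. Descriptive laboratory tables can understate hepatic and renal abnormalities, mainly for elevations not recorded as adverse events. How many such elevations there would be cannot be estimated from the documents. The conclusion assumes the rule is followed literally and that worst grades are not already derived from laboratory values under a convention the documents do not state. No formal comparison of toxicity is planned, and the primary endpoint, sample size and error rates do not depend on this rule. It is a minor point, worth correcting before the tables are programmed.

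**What to change.** In section 8.2.5, replace the nadir with *the worst value in the direction of toxicity*, per cycle and per patient, and give the direction for each test:

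- lowest: blood counts, albumin and creatinine clearance;
- highest: ALT, AST, bilirubin, serum creatinine, alkaline phosphatase, GGT and LDH (BUN and uric acid, also in the panel, fit here);
- both directions: electrolytes and glucose.

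Add that worst laboratory CTCAE grades are derived from these values, whether or not the finding was reported as an adverse event. The nadir wording for blood counts in section 7.3.2 can stay.

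The cost is one or two sentences in the SAP and the matching table specification. Data collection and trial conduct do not change.
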